7.3.2 Aim 2 Exposures

The exposure of interest is oxygen therapy versus no oxygen therapy among patients with fibrosing ILD and is defined based on evidence of oxygen therapy following ILD diagnosis, as described in Section 7.2.3.

7.3.3 Aim 2 Outcomes

7.3.3.1 Primary Outcomes

All primary outcomes will be measured in the Aim 2 and Further Aim follow-up period, unless specified otherwise.

- **Time to disease progression**—Pulmonary function test (PFT) results will be captured as available in the database in the pre-ILD baseline, pre-index baseline, and Aim 2 follow-up periods among the subset of patients who have EHR data during the same

time of ILD diagnosis and oxygen therapy. All valid result values will be captured. Values closest to the fibrosing ILD diagnosis date will be reported for the pre-ILD baseline period; values closest to the index date will be reported for the pre-index baseline period; the latest values prior to the end of follow-up will be reported for the Aim 2 follow-up period. PFT tests may potentially include forced expiratory volume in 1 second (FEV₁), forced vital capacity (FVC), FEV₁/FVC ratio, lung volumes, and diffusing capacity for carbon monoxide (DLCO), as available.

Among patients or matched pairs with FVC results in the pre-index and follow-up periods, disease progression will be defined as a 10% relative change between the pre-index value and the follow-up value. Time to disease progression will be reported. Additionally, time in days from pre-index FVC result to the index date and from index date to follow-up FVC result will be reported.

- **Time to all-cause mortality**—We will assign the date of death as the 15th day in the month of death. Time to all-cause mortality will be calculated as time between index date and mortality date.

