date (i.e., similar to the matched oxygen therapy patient in time from the fibrosing ILD diagnosis date to the index date, and during the same continuous enrollment period as the fibrosing ILD diagnosis date).

NOTE: Following review of results from Aim 1, the study team will determine whether continuous enrollment criteria for Aim 2 and Further Aim requires revision.

Variables:	
Aim 1
 
Outcomes: time to initiation of oxygen therapy; time to sustained oxygen therapy use; sustained oxygen therapy use within the first 12 months of follow-up
 
Baseline covariates: demographic characteristics (age, sex, race/ethnicity, geographic region, insurance type, index year), clinical characteristics (underlying ILD type; respiratory diseases; other clinical characteristics; Quan-Charlson comorbidity score; Agency for Health Research and Quality [AHRQ] comorbid conditions; smoking; pulmonary rehabilitation) healthcare utilization characteristics (provider specialty; medication use; all-cause HCRU; all-cause health care costs)
 
Stratification: IPF vs non-IPF ILD
 
Aim 2 [REDACTED]
 
Exposure: oxygen therapy vs no oxygen therapy
 
Primary Outcomes: Time to disease progression; time to all-cause mortality; time to hypoxemia, time to acute exacerbations, counts of acute exacerbations
 
[REDACTED]
 
Baseline covariates: demographic characteristics (index year, age, sex, race/ethnicity, geographic region, insurance type), clinical characteristics (underlying ILD type; respiratory diseases; other clinical characteristics; Quan-Charlson comorbidity score; AHRQ comorbid conditions; smoking; pulmonary rehabilitation) healthcare utilization characteristics (provider specialty; medication use; all-cause HCRU; all-cause health care costs)

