7. RESEARCH METHODS

7.1 STUDY DESIGN

[figure not shown]
This is a non-interventional study of patients enrolled in a commercial, Medicaid, or Medicare plan, using existing administrative claims and EHR data in Optum's Market Clarity Integrated Claims + Clinical database for the period of 01 October 2015 through 30 June 2022 (study period). The study period may be extended through latest data available at the time of study implementation to increase study sample.

To describe the initiation and use of oxygen therapy after first fibrosing ILD diagnosis (**Aim 1**), patients aged ≥ 18 years with newly diagnosed fibrosing ILD will be identified from 01 October 2016 through 30 June 2022 (patient identification period). A schematic of the observation and identification periods is presented in Figure 1. Patients will be required to have 12 months of baseline continuous enrollment prior to fibrosing ILD diagnosis for collecting patient demographics and clinical characteristics. The pre-ILD baseline period will also be used to describe baseline prevalence of oxygen therapy use. Patients will be followed for a variable period from the fibrosing ILD diagnosis date (Section 7.2.2) until the earlier of disenrollment from the health plan, end of study period, or death. Oxygen therapy use will be described, and results will be stratified by underlying cause of fibrosis (e.g., IPF vs non-IPF ILD). Factors associated with initiation of oxygen therapy will be assessed using multivariable methods.

To assess the impact of oxygen therapy use on outcomes (**Aim 2 and Further Aim**), patients with fibrosing ILD who initiated oxygen therapy will be propensity score matched to those who did not yet initiate oxygen therapy. A schematic of the observation and identification periods is presented in Figure 2. The index date will be defined as the date of oxygen therapy initiation for oxygen therapy cohort, or a date that is eligible for index and is similar to the

[figure not shown]
matched case's index date for no oxygen therapy cohort. Disease progression, acute exacerbations, health care resource utilization (HCRU), and health care costs in the Aim 2 follow-up period will be described and compared between matched cohorts. Outcomes will be modelled using multivariable methods.

Figure 1. Observation and Identification Periods: Aim 1

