7.3 VARIABLES

Variables related to the study period will be defined as follows:

Aim 1

- **Fibrosing ILD diagnosis date**—The first ILD diagnosis date for patients with ≥ 2 fibrosing ILD diagnoses on different dates and within 365 days. The fibrosing ILD diagnosis date is the first day of follow-up observation time for Aim 1.
- **Pre-ILD baseline period**—The 12-month period prior to the fibrosing ILD diagnosis date.
- **Aim 1 follow-up period**—The variable period starting on the fibrosing ILD diagnosis date and continuing until the earliest of the following: disenrollment from the health plan, death, or end of the study period. The Aim 1 follow-up period will be used to assess Aim 1 outcomes.
 - **All-cause mortality**—Death will be used as a censoring event and is further defined in Section 7.3.3.1.

Aim 2

- **Index date**—For the oxygen therapy cohort, the first date following the fibrosing ILD diagnosis date with a claim with diagnosis for oxygen therapy; for the no oxygen therapy cohort, a date within the same continuous enrollment period as the fibrosing ILD diagnosis date that is similar to the matched oxygen therapy patient in time from fibrosing ILD to index date. The index date is the first day of follow-up observation time for Aim 2 and Further Aim.
- **Pre-index baseline period**—The 12-month period prior to the index date.
- **Aim 2 follow-up period**—The variable period starting on the index date until the earliest of the following: disenrollment from the health plan, death, or the end of the study period. Matched pairs will be given the same duration of follow-up. The Aim 2 follow-up period will be used to assess Aim 2 and Further Aim outcomes.
 - **All-cause mortality**—Death will be used as a censoring event and is further defined in Section 7.3.3.1.

An overview of the analytic study variables and the study periods for which each analytic variable will be reported is provided in Table 1. Additional variable information is provided in Sections 7.3.1 to 7.3.4.

Table 1. Analytic Variables by Data Source and Time Period

Characteristic	Data source		Aim 1 time period		Aim 2 time period	
	Claims*	EHR	Pre-ILD baseline	Follow-up	Pre-index baseline	Follow-up
Aim 1 outcomes						
Oxygen therapy (time to initiation, sustained oxygen therapy use)		X		X	X	
Aim 2 outcomes						
Disease progression	X	X				X
All-cause mortality	X					X
Hypoxemia	X	X	X		X	X
Acute exacerbations	X	X				X
Patient characteristics†						
Index year	X		X		X	

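### Time to disease progression has no common FVC assessment time, so unequal testing after index could create a difference between cohorts; test frequency by cohort and a fixed-time sensitivity analysis would guard against this

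*Combined protocol and SAP*

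**What the plan says.** The Abstract lists the Aim 2 primary outcomes as beginning "Time to disease progression; time to all-cause mortality; time to hypoxemia". Section 7.1 says disease progression, among other outcomes, "will be described and compared between matched cohorts".

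Section 7.3.3.1 takes the measurements from routine care: "Pulmonary function test (PFT) results will be captured as available in the database in the pre-ILD baseline, pre-index baseline, and Aim 2 follow-up periods". For follow-up, "the latest values prior to the end of follow-up will be reported for the Aim 2 follow-up period". The analysed set is given as "Among patients or matched pairs with FVC results in the pre-index and follow-up periods", and in that set "disease progression will be defined as a 10% relative change between the pre-index value and the follow-up value". The text does not say whether the event date is that of the latest test or of the first test to cross 10%. It also does not say when patients without progression are censored.

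Two provisions bear on test timing. Section 7.3: "Matched pairs will be given the same duration of follow-up". Section 7.3.3.1: "time in days from pre-index FVC result to the index date and from index date to follow-up FVC result will be reported". The limitations in Section 7.8 mention reliance on available EHR values, but not a difference in testing between cohorts. Table 1 has no variable for the intensity of FVC testing during follow-up.

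**The concern.** Progression can be observed only on a day when spirometry is done, and here those days follow routine care. The index date of the oxygen cohort is itself a care event. It could plausibly be followed by more tests (closer specialist follow-up) or by fewer (a less mobile patient). Matching uses variables measured before index, so it cannot balance a difference in testing that arises afterwards.

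Unequal testing acts differently under the two readings of the definition:

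- **First crossing.** The more-tested cohort has its crossings found sooner, and has more chances for one noisy value to pass 10%.
- **Latest value.** Only one value per patient counts, so the extra chances disappear. But the last test of a more-tested patient falls later in follow-up, when more decline has accrued.

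At stake is whether a difference in progression between cohorts reflects lung function or the testing pattern.

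**Working it through.** The documents state no power, alpha, event count or test frequency for this outcome, so there is no planned figure to reproduce. The check is a simulation in which decline is identical in both cohorts and only the test interval differs.

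**Inputs, all assumed:** 20,000 patients per arm; mean FVC decline 5% of baseline per year with a between-patient SD of 5 points per year; test error SD 3%; follow-up shared within pair (0.25 year plus an exponential time with mean 1.5 years, capped at 5 years); tests every 3, 6 or 12 months with a random start. **Event:** a fall of at least 10% from the pre-index value. Hazard ratios (HR) come from a Cox model with cohort as the only covariate, more-tested against less-tested.

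| Test interval, months | First crossing: HR | First crossing: progressed by 12 months | Latest value: progressed, pairs with both tested | Latest value: mean days from index to last FVC, same pairs | Latest value: HR, non-progressors censored at end of follow-up | Latest value: HR, censored at last test |
|---|---|---|---|---|---|---|
| 6 vs 6 (control) | 1.00 | 21.4% vs 21.4% | 33.7% vs 33.7% | 566 vs 566 | 1.03 | 1.02 |
| 3 vs 6 | 1.20 | 28.7% vs 21.1% | 34.9% vs 32.8% | 588 vs 545 | 1.03 | 0.95 |
| 6 vs 12 | 1.17 | 21.1% vs 14.5% | 36.8% vs 31.7% | 617 vs 541 | 1.07 | 0.93 |
| 3 vs 12 | 1.39 | 28.5% vs 13.9% | 38.9% vs 31.5% | 650 vs 530 | 1.11 | 0.91 |

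**First crossing.** Varying decline from 3% to 10% per year and test error from 0 to 5%, the HR for the more-tested cohort ran from 1.07 to 1.67. At a nominal 5% level, the false-positive rate was about 20% with 250 per arm and 48% to 61% with 1,000 per arm, against 3.5% to 3.8% with equal testing. A separate simulation used other assumptions (SD 6% per year, measurement CV 4%, 2 years of follow-up, irregular test gaps). It gave HR 1.12 for mean intervals of 4.8 vs 6 months, 1.22 for 4 vs 6, 1.37 for 3 vs 6 and 1.42 for 4 vs 8.

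**Latest value.** The shifts in tested pairs are 34.9 − 32.8 = 2.1, 36.8 − 31.7 = 5.1 and 38.9 − 31.5 = 7.4 points. They arise because the last test is later by 588 − 545 = 43, 617 − 541 = 76 and 650 − 530 = 120 days. At 5% per year that is 5 × 43/365 = 0.6, 5 × 76/365 = 1.0 and 5 × 120/365 = 1.6 points of extra mean decline.

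The denominator matters. Among all tested patients rather than tested pairs, the proportions were 34.0% vs 32.6%, 32.2% vs 31.9% and 33.7% vs 31.8%, shifts of only 1.4, 0.3 and 1.9 points. The less-tested cohort then loses its patients with short follow-up, which partly offsets the effect.

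The HRs in the last two columns are for all tested patients. An HR of 1.03 is within simulation noise, since the control also gave 1.03. False-positive rates of tests based on the latest value did not exceed 8%.

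**Fixed time.** In the first simulation, using the value nearest 12 months (within 2 months), 25.9% vs 26.1%, 25.9% vs 26.2% and 25.7% vs 25.7% progressed, with false-positive rates of 3.5% to 6.0%. In the second (9 to 15 months), the proportion was 26.6% to 26.8% at every mean interval from 3 to 8 months. An interval-censored Weibull model in the first simulation gave HR 1.00 to 1.01 without test error but 1.06 to 1.20 with 3% error, so it does not remove the problem.

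**Limit of the fixed-time version.** These fixed-time results assume that testing does not depend on decline. When faster decliners were tested more (test rate multiplied by exp(0.5) per SD of slope, second simulation), the fixed-time proportion was 29.9% at 3-month and 33.7% at 8-month testing. A repeat run gave 30.0% and 34.1%.

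**The case against.** The strongest reply has four parts.

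- **The premise cannot be checked.** The documents give no FVC frequency, overall or by cohort. A reader might infer that the comparison is biased, or that a null oxygen effect will appear as harm or benefit. The documents do not support that: without unequal testing there is no such bias, and its direction is unknown. This part stands and makes the point conditional.
- **The large hazard ratios belong to a rule the plan does not state.** A reader might apply HR 1.2 to 1.4 to this study. But Section 7.3.3.1 speaks of the latest follow-up value and of a single follow-up value, and never of a first crossing. Under that wording the HR bias is small and can run either way. This part stands; what remains is the shift in the proportion progressing.
- **There are safeguards.** Equal pair follow-up fixes the length of the window, but not the test dates within it. Days from index to the follow-up FVC would show much of an imbalance, but nothing in the published text uses them to restrict or adjust. These are partial answers.
- **The Aim 2 analysis is not visible.** Section 7.2.3 refers to Section 7.6.2.2, while the published text goes from 7.6.1.3 to 7.7. A fixed-time analysis or an adjustment for testing may be specified there. This stands, so the point covers the outcome definition only.

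**Conclusion.** The point holds in conditional form. As published, the outcome has no common assessment time. If testing after index differs between cohorts, a difference in progression can arise with identical decline, and the two existing provisions may reveal this but do not correct it.

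Under the assumed values, the bias is clear for a first-crossing rule: HR about 1.2 to 1.4 for the more-tested cohort, inverting if the oxygen cohort is the less-tested one. Under the latest-value wording, the proportion progressing shifts by about 2 to 7 points in tested pairs and by less among all tested patients. The HR bias there is small, and its sign depends on the censoring rule. All sizes are illustrative, because test intervals, decline, variability and test error are not in the documents.

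A reader might also infer that a fixed-time result would settle the matter. It would not, because it is biased too when testing depends on the rate of decline.

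**What to change.** In Section 7.3.3.1:

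1. Report FVC tests per person-year after index, by cohort.
2. Add a sensitivity analysis comparing the cohorts on a relative FVC decline of 10% or more at the single value closest to month 12 after index, for example within 9 to 15 months.
3. Report the share of each cohort with a value in that window, and the baseline characteristics of those patients.
4. State that the time-to-event result will be interpreted with caution if the two analyses disagree. Agreement should not be a condition for drawing a conclusion, because the fixed-time analysis can itself be biased.

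The cost is one extra analysis and a few descriptive rows, from values the plan already captures. The downsides are lower precision (in the second simulation 53% to 86% of patients had a value in the window, depending on test frequency) and possible selection of the patients who happen to be tested then.

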*The ILD diagnosis date will be defined as the first date of a claim with diagnosis for fibrosing ILD during the identification period. Patients will be followed from the fibrosing ILD diagnosis date until the earlier of disenrollment from the health plan, death, or end of the study period. Figure is not to scale and is for illustrative purposes only.

Figure 2. Observation and Identification Periods: Aim 2

*The fibrosing ILD diagnosis date will be before the index date and may be before or during the pre-index baseline period.

†The index date will be defined as the first date of a claim with oxygen therapy (oxygen therapy cohort), or a date that is eligible for index and is similar to the matched case's index date (no oxygen therapy cohort).

Patients will be followed from the index date until the earlier of disenrollment from the health plan, death, or end of the study period.

Figure is not to scale and is for illustrative purposes only.

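### The FVC progression outcome has two subset rules that do not match, and the rule requiring EHR data at ILD diagnosis can exclude patients who have both FVC values the outcome needs

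*Combined protocol and SAP*

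**What the plan says.** Time to disease progression is a primary Aim 2 outcome, and Section 7.3.3.1 describes its data in two steps.

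The first step covers capture of pulmonary function tests, FVC included, in three periods: pre-ILD baseline, pre-index baseline and Aim 2 follow-up. Capture is limited to results "among the subset of patients who have EHR data during the same" "time of ILD diagnosis and oxygen therapy" (one clause, running over a page break). Diagnosis-time results have a stated use: "Values closest to the fibrosing ILD diagnosis date will be reported for the pre-ILD baseline period".

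The second step defines the outcome and has its own evaluability rule: "Among patients or matched pairs with FVC results in the pre-index and follow-up periods", with progression taken as a "10% relative change between the pre-index value and the follow-up value".

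Two design features bear on this. Under Section 7.1, oxygen initiators are "propensity score matched to those who did not yet initiate oxygen therapy"; Sections 7.2.3 and 7.3 give these controls an assigned index date. The note to Figure 2 adds: "The fibrosing ILD diagnosis date will be before the index date and may be before or during the pre-index baseline period". Section 7.3 sets the pre-index baseline at 12 months.

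**The concern.** The capture rule acts before the outcome rule. An FVC that is never captured cannot enter the progression comparison, so the narrower of the two rules decides who is analysed. The capture rule is tied to diagnosis and oxygen therapy, whereas the outcome is tied to the index date.

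Two things could follow. The oxygen condition refers to an event that a never-treated control does not have, so a programmer must decide what it means in one of the two cohorts. The diagnosis condition can remove patients whose data are complete for the comparison being made. What is at stake is precision for a primary outcome and, if the rule is applied differently in the two cohorts, the comparability of the evaluable sets.

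**Working it through.** The plan states no sample size, event count or power for the FVC outcome, so it has no figure to reproduce. The check is a comparison of the two rules, followed by an illustration.

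**Comparison of the rules**

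| Item | Capture rule | Progression rule |
|---|---|---|
| Data required | EHR data at ILD diagnosis and at oxygen therapy | FVC in pre-index baseline and in follow-up |
| Anchor, oxygen cohort | Diagnosis date and oxygen start (the index date) | Index date |
| Anchor, no-oxygen cohort | Diagnosis date; no oxygen date for never-treated patients | Assigned index date |
| Diagnosis-time data needed? | Yes | No |

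*Oxygen condition.* In the oxygen cohort, oxygen start and index date are the same day. In the no-oxygen cohort only the assigned index date exists. If oxygen therapy is read as the index date, the condition applies to both cohorts and adds little to the requirement for FVC values on either side of that date. If it is read literally, no date exists for a never-treated control.

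*Diagnosis condition.* Identification runs from 01 October 2016 to 30 June 2022, which is 69 months, so diagnosis can precede index by much more than the 12-month baseline. Take a patient diagnosed 24 months before index whose EHR record begins 10 months before index, with one FVC after that point and one in follow-up. The progression rule is met and the capture rule is not. This holds whichever way the oxygen condition is read. Section 7.8 states that only part of the population has EHR data, so such gaps cannot be ruled out.

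**Illustration by assumption**

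Let q be the share of patients with both required FVC values who also have EHR data at diagnosis. The documents give no value for q.

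- By patient: the evaluable number falls to a fraction q. If events fall in proportion, CI width grows by 1/√q.
- By matched pair, both members required and independent: the share of pairs lost is 1 − q².

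| q | Patients lost, 1 − q | CI factor, 1/√q | Pairs lost, 1 − q² |
|---|---|---|---|
| 1.0 | 0% | 1.00 | 0% |
| 0.8 | 20% | 1/√0.8 = 1.12 | 1 − 0.64 = 36% |
| 0.5 | 50% | 1/√0.5 = 1.41 | 1 − 0.25 = 75% |

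Both loss columns are shown because the plan mentions patients or matched pairs without choosing between them.

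**The case against.** The strongest reply is that this is loose wording and no more. The outcome already has an index-anchored rule for both cohorts, and its mention of matched pairs presupposes evaluable controls. Section 7.3.1.1 equates index date with oxygen initiation date, though within Aim 1. It is therefore natural to read oxygen therapy as the index date. The clause also covers three periods, one of which is the pre-ILD baseline, so naming diagnosis has a purpose: it gives a single population for the whole pulmonary function description. The Aim 2 analysis section, to which Section 7.2.3 refers for matching, is not in the available text and may settle the subset.

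Much of this stands. A reader might infer that the rule leaves no controls, or only those who later start oxygen. That follows only from the literal reading, which the reference to matched pairs makes unlikely. A reader might also infer that diagnosis-time values are collected for nothing; they are reported for the pre-ILD baseline and are unused only in the progression definition.

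A reader might turn to Table 3, where 34,299 of 212,466 adults (16.1%) remain after the enrollment and EHR activity requirements, as a measure of the loss. It cannot serve as one: it counts oxygen users only, mixes enrollment loss with EHR loss, and gives no FVC or control count. Nor do the documents show that this is the smallest analysis set, since they give no number for any outcome subset.

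The reply does not remove the diagnosis condition. A common population for a descriptive table does not justify limiting a primary outcome to patients with data that the outcome does not use.

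**Conclusion.** The point holds in limited form. Section 7.3.3.1 contains two subset rules for one primary outcome, and they do not match. The oxygen condition has no date in the no-oxygen cohort as worded; reading it as the index date resolves that part. The diagnosis condition is unnecessary for the progression comparison under either reading and can exclude patients or pairs with both required FVC values.

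Neither the size nor the direction of the effect can be derived. The factors of 1.12 to 1.41, and pair losses of 36% to 75%, rest wholly on assumed values of q between 0.8 and 0.5; the pair figures also assume independence within pairs. If nearly all patients with an FVC pair have EHR data at diagnosis, the effect is negligible. The documents do not support a claim of bias in a particular direction. The clause should still be corrected, because it is a stated rule that decides who is analysed for a primary outcome.

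**What to change.** For the progression outcome, replace the capture clause in Section 7.3.3.1 with: patients in either cohort who have EHR data in the 12-month pre-index baseline and in the Aim 2 follow-up period, with both windows anchored on the index date (assigned, for the no-oxygen cohort). Keep diagnosis-time pulmonary function values for the descriptive pre-ILD summary only. State whether evaluability is judged by patient or by matched pair, and report the evaluable numbers by cohort.

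The cost is a few lines of text and no new data. The one small downside is that the pre-ILD summary will have a different denominator from the outcome, which should be shown in its table.

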7.2.3 Study population: Aim 2 [REDACTED]

The analysis for Aim 2 and Further Aim will include patients identified for Aim 1 in Section 7.2.2 who meet the following additional selection criteria. Final oxygen therapy cohorts will be determined during the propensity score matching (PSM) procedure outlined in Section 7.6.2.2.

- **Oxygen therapy cohort**

- ILD patients with ≥ 1 medical claim for oxygen therapy after fibrosing ILD diagnosis. The ***index date*** will be defined as the first date of a claim for oxygen therapy.

- **No oxygen therapy cohort**
 - Matched to a patient in the oxygen therapy cohort. The **index date** will be assigned as a date that is eligible to set an index date (i.e., similar to the matched oxygen therapy patient in time from the fibrosing ILD diagnosis date to the index date, and during the same continuous enrollment period as the fibrosing ILD diagnosis date).

NOTE: Following review of results from Aim 1, the study team will determine whether criteria for Aim 2 and Further Aim require revision.

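### FVC lost before the index date counts towards the 10% progression threshold, because the baseline FVC may be up to 12 months old and an FVC on the index date falls in follow-up

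*Combined protocol and SAP*

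**What the plan says.** Section 7.3 fixes the periods. The baseline window is defined as "Pre-index baseline period—The 12-month period prior to the index date". For follow-up, "The index date is the first day of follow-up observation time for Aim 2 and Further Aim". In the oxygen cohort the index date is the first oxygen claim (section 7.2.3). In the comparison cohort it is an assigned date, at a similar time since the fibrosing ILD diagnosis as in the matched oxygen patient.

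Section 7.3.3.1 then selects the FVC values. For baseline, "values closest to the index date will be reported for the pre-index baseline period". For follow-up, "the latest values prior to the end of follow-up will be reported for the Aim 2 follow-up period". Progression is a 10% relative change between the two. No maximum age within the 12 months is set for the baseline FVC, and no minimum time after index for the follow-up FVC. On the intervals, the section says "time in days from pre-index FVC result to the index date and from index date to follow-up FVC result will be reported".

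The readable covariate lists (section 7.3.5 and the abstract) contain neither the pre-index FVC level nor its age. Section 7.8 does not discuss test timing. Section 7.6.2, to which section 7.2.3 refers for the matching, is not in the readable text.

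**The concern.** The change in FVC accrues from the baseline test, while follow-up runs from the index date. The protocol does not spell out the start of the progression clock. Aim 2 follow-up starts at index, though, and mortality in the same section is timed from index. Any decline between the baseline test and index is thus credited to follow-up. An FVC taken on the index date, which would be the most current pre-treatment value, is excluded from baseline and placed in follow-up.

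The study asks whether oxygen leads to better or worse outcomes. Decline that occurred before oxygen cannot be an effect of oxygen. If the cohorts differ in how old their baselines are, or in how fast FVC fell before index, part of the difference in time to progression would come from test timing or from the deterioration that led to oxygen.

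**Working it through.** The plan gives no sample size, event rate or effect size for this outcome, so there is no figure to reproduce. The definitions can be checked directly. The size can only be illustrated, with 10% relative change read as a 10% fall.

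**1. Definitions side by side.** The baseline FVC lies somewhere in the 12 months before index, and the value nearest to index is taken. Index is day 1 of follow-up. An index-date FVC is therefore never a baseline. It becomes the compared value in two cases: the patient has no later FVC, or time to progression uses the first value that meets the threshold. The text does not say which value dates the event.

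**2. Loss used up before index.** Loss = 1 − (1 − r)^(gap/12), with r the annual relative decline (assumed) and the gap in months:

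| r per year | 3 months | 6 months | 12 months |
|---|---|---|---|
| 5% | 1.3% | 2.5% | 5.0% |
| 10% | 2.6% | 5.1% | 10.0% |
| 20% | 5.4% | 10.6% | 20.0% |

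At 10% a year with a 12-month-old baseline, the whole threshold is reached at index.

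**3. Different baseline ages, same decline.** Assumptions: decline r ~ N(6, 5) % per year, truncated to −5 to 30; measurement SD 3%. A patient has crossed at t years after index if r × (gap + t) + noise ≥ 10, with the gap in years. Simulated share crossed at t = 1:

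| Baseline age | Crossed | Excess over 1 month |
|---|---|---|
| 1 month | 29% | – |
| evenly over 0-3 months | 31% | about 2 points |
| evenly over 0-6 months | 36% | about 7 |
| closest of three tests in 12 months | 36% | about 7 |
| closest of two tests | 39% | about 10 |
| evenly over 0-12 months | 44% | about 15 |

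In the last row, 7% have already crossed at index. With a mean decline of 4% or 10% a year instead of 6%, the last excess is 12.8 or 15.7 points.

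**4. Same baseline age, different pre-index decline.** P(progression) = 1 − Φ((10 − m)/SD), where m = pre-index rate × gap/12 + post-index rate × t/12. Assumptions: no oxygen effect; post-index decline 6% a year in both cohorts; pre-index decline 10% (oxygen) and 4% (no oxygen) a year; SD 5 points; FVC at t = 6 months, so the post-index part of m is 3.

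- 12-month-old baseline: m = 13 and 7, giving 72.6% against 27.4%.
- 6 months: m = 8 and 5, giving 34.5% against 15.9%.
- 3 months: m = 5.5 and 4, giving 18.4% against 11.5%.
- Baseline at index: m = 3 in both, giving 8.1% in both.

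If the pre-index rates are equal (6% a year, 12-month-old baseline), m = 9 in both cohorts and progression is 42.1% in each. The rate is inflated, but the comparison is not biased.

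**The case against.** Several counter-arguments have force.

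- **The Aim 2 analysis cannot be read.** A reader might infer that the plan reports the gaps and does nothing more with them. The documents do not support that: section 7.1 says Aim 2 outcomes will be modelled with multivariable methods, and the model itself is not visible. This stands. However, covariate adjustment would not by itself reclassify an index-date FVC, because that follows from section 7.3.
- **The latest follow-up value is reported.** A reader might infer that any index-date FVC can produce progression on day 0. If only the latest value is compared, that happens only when no later FVC exists. This stands. The age of the baseline enters the change under either reading.
- **Twelve months is a maximum.** The closest value is chosen, so a patient tested more than once has a shorter gap. The 15-point contrast is near a worst case, and the documents give no distribution of test timing. The simulation also scores everyone at a fixed time, whereas the latest values will fall at varying times. This stands.
- **Both cohorts have the same window.** A difference in baseline age or pre-index decline is an inference. It is plausible, because starting oxygen is a clinical decision while the comparison date is assigned, but it is not documented. The effects also oppose each other: tests near the oxygen start shorten the gap, while excluding start-date tests from baseline lengthens it.
- **Both intervals will be reported.** That lets readers see an imbalance. It does not correct one.

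**Conclusion.** The point holds in limited form, with moderate confidence. By the protocol's own definitions, FVC lost in up to 12 months before index counts towards progression after it, and an index-date FVC is treated as follow-up. Progression is therefore inflated in both cohorts.

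A reader might go further and infer that the comparison is biased for or against oxygen. The documents do not show this. It requires baseline age or pre-index decline to differ between cohorts, and the net direction is unknown. If baseline ages differ, the illustrative 12-month artefact is about 2 to 15 points, and all rates and SDs behind that range are assumptions. The step 4 figures are equally conditional, resting on assumed pre-index rates of 10% and 4% a year.

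This should be changed before analysis: the outcome is primary, the rule is explicit, and the correction uses data already captured.

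**What to change.** In section 7.3.3.1:

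1. Count an FVC on the index date as the pre-index value, and require the follow-up FVC to be after the index date. State whether time to progression is dated by the first qualifying value or by the latest one.
2. Unless section 7.6.2 already does so, include the pre-index FVC level and the days from that FVC to index as covariates in the progression comparison.
3. Add a sensitivity analysis limited to patients with a recent pre-index FVC, for example within 90 days. That cut-off is an assumption; the documents give no basis for a particular value.

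Item 2 addresses differing baseline age but not differing pre-index decline. Item 3 reduces both without removing them: in step 4 a 3-month-old baseline still leaves 18.4 − 11.5 = 6.9 points, compared with 72.6 − 27.4 = 45.2 at 12 months.

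The cost is a change of protocol wording and two covariates from data already captured. The sensitivity analysis uses a smaller and less precise FVC subset, and patients whose only follow-up FVC is on the index date drop out of the comparison.
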